#### *Eligible Participants and Consent*

Evaluating IR and making correlations between exposure to MRI or environmental magnets and symptoms and radiographic changes (when available) will require the patient or family to complete a brief questionnaire. It will then require the study team and delegated providers to check the valve setting before and after MRI, and to gather clinical information from the medical record and from the current clinical evaluation.

Each patient's initial enrollment will require the acquisition of an informed consent, which will cover all future evaluations of IR during the three year study period for that patient. However, every time a patient enrolled in the study encounters the neurosurgical service, all study steps will be performed, including the valve check before and after MRI, the participant's completion of the questionnaire, and the research staff's completion of the data sheets.

#### *Sequence of Evaluations*

Once informed consent is obtained, eligible patients will complete the questionnaire and eligible study personnel will check the current valve setting transcutaneously (5-15 seconds). Ideally, the valve check will be performed after

Date: 4/19/2016 V.2  
Principal Investigator: [name]  
Application Number: IRB00093490

## **JHM IRB - eForm A – Protocol**

the questionnaire is complete, in order to blind the family members to whether or not an IR has occurred. If checking the valve prior to questionnaire completion is necessary for clinical reasons, the patient and their family will be kept unaware of the valve setting. For patients undergoing MRI as part of their evaluation, their valve will be rechecked shortly after the MRI and the data recorded. Study personnel will then complete the two-page data sheet, which requires the compilation of data acquired during a routine neurosurgical evaluation. Any adjustments to the valve, which will be dictated by the routine care of the patient, will be recorded as well.

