## **JHM IRB - eForm A – Protocol**

whether or not they feel the child is having symptoms of shunt malfunction, as well as their knowledge of the MRI susceptibility of their valve. Specific questions about the frequency and proximity of exposure to devices and circumstances that have previously been associated with IR will also be assessed.

Study personnel will check the valve setting, without divulging any information to the family about where the valve is currently set, in order to minimize patient or family bias when they are completing the questionnaire.

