### *Shunt Data Sheet Completion by Study Personnel*

A wide range of clinical factors routinely gathered during neurosurgical evaluations will be recorded on a two-page data sheet at the time of each evaluation performed as part of this study. Data regarding documented valve settings, previous purposeful reprogramming, signs and symptoms of shunt malfunction, and the radiographic evaluation of the patient's ventricles will be recorded (see attached study personnel data sheet). Only factors routinely evaluated during typical neurosurgical evaluations will be recorded.

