### *Statistical Considerations*

The statistical analysis will be supervised and performed by [name] and his colleagues at the ACH/JHM CTRO. Demographic and clinical characteristics will be reported by IR status and compared using  $\chi^2$  or Fishers exact tests for categorical measures and t-test or Mann-Whitney U tests for continuous measures.

Aim #1: The frequency of IR will be calculated as the number of hydrocephalic children with Strata CSF shunt valves who had IR divided by the total number of hydrocephalic children with Strata CSF shunt valves.

Aim #2: The association between the field strength of MRI scanning and IR will be determined using unadjusted and adjusted generalized estimating equation models that account for multiple evaluations of participants. IR will be a binary outcome variable (IR present vs IR absent) and the field strength of MRI (3T vs 1.5T) will be the predictor variable. The adjusted model will include potential confounders that will be selected based on prior knowledge of factors established to be associated with IR as well as additional factors with p-value <0.1 in univariate analyses.

Aim #3: We will compare the proportion of patients with signs, symptoms or radiographic changes suggestive of shunt malfunction between the IR and no IR groups using  $\chi^2$  or Fishers exact tests for categorical measures and t-test or Mann-Whitney U tests for continuous measures

Aim #4: The association between devices that may have sufficient electromagnetic charge to affect programmable valves and IR will be determined using unadjusted and

Date: 4/19/2016 V.2  
Principal Investigator: [name]  
Application Number: IRB00093490

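### Staff who record the Aim 3 signs, symptoms and ventricular findings are not kept unaware of the valve reading; a reordered form and a tick-box would be a cheap improvement

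*Combined protocol and SAP*

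**What the plan says.** All references are to the combined protocol and SAP.

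- **Who is blinded.** Under Sequence of Evaluations (section 4), the valve is ideally checked after the questionnaire, "in order to blind the family members to whether or not an IR has occurred". If the check has to come first, "the patient and their family will be kept unaware of the valve setting". The section on the questionnaire and initial valve check repeats this: "Study personnel will check the valve setting, without divulging any information to the family about where the valve is currently set".
- **When staff record.** Sequence of Evaluations continues, after the valve check and any recheck following MRI: "Study personnel will then complete the two-page data sheet". The sheet is described there as compiling what the routine evaluation has produced. Eligible Participants and Consent gives the same order. After the questionnaire, "It will then require the study team and delegated providers to check the valve setting before and after MRI", and then to collect clinical information from the record and the current evaluation.
- **What the sheet holds.** Under Shunt Data Sheet Completion by Study Personnel, the sheet records valve settings and earlier deliberate reprogramming, together with "signs and symptoms of shunt malfunction, and the radiographic evaluation" of the ventricles.
- **Who does it.** Under Personnel Performing Evaluations, most evaluations fall to the treating neurosurgical team. MRI staff are expected to give the questionnaire and take the first reading when imaging precedes contact with that team.
- **How it is analysed.** For Aim 3, the Statistical Considerations section states: "We will compare the proportion of patients with signs, symptoms or radiographic changes suggestive of shunt malfunction between the IR and no IR groups". The tests named are chi-square or Fisher for categorical measures and t or Mann-Whitney for continuous ones.

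**The concern.** The plan recognises that knowing the reading can colour what is reported, and it orders the steps so that the family's answers are protected. The same reasoning applies to staff. Whether a headache counts as a sign of malfunction, or a ventricle as changed, is partly a matter of judgement. A recorder who knows that the valve has moved may ask further or call a borderline finding positive.

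Hypotheses 3a and 3b predict more findings with IR, so differential recording of this kind would tend to push the comparison in the predicted direction. The Aim 3 tests compare the two groups directly and cannot separate a true excess from an excess of recording. The data described do not include whether the recorder knew the reading, so the problem could not be examined afterwards.

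**Working it through.** The plan states no figure on this point, so there is none to reproduce. The check sets the passages side by side.

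| Aim 3 ingredient | Where recorded | Kept from the reading? |
|---|---|---|
| Symptoms as the family sees them | Questionnaire | Yes, by order of steps or by withholding the reading |
| Signs and symptoms recorded by staff | Data sheet, after the valve check | No provision |
| Ventricular findings | Data sheet, after the valve check | No provision |
| IR status (reading against documented setting and deliberate changes) | Same data sheet | Not applicable |

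The second and third rows are the gap. No section keeps the reading from the person completing the sheet, asks for signs and symptoms to be written down first, or provides for ventricles to be assessed without knowledge of valve status.

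**Illustration only.** The following shows how sensitive the Aim 3 test would be to differential recording. It does not estimate the bias.

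- From the documents: N = 996 and IR of 5% (Sample Size Estimation); IR as high as 20%, described there as anecdotal (Limited Previous Prevalence Studies).
- Assumed: no true association; findings recorded in 20% without IR (p2); 25% or 30% with IR (p1) because the reading is known; independent records; two-sided alpha 0.05, which the plan states for Aim 4 and not for Aim 3.

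Apparent odds ratio: (0.25/0.75)/(0.20/0.80) = 1.33; (0.30/0.70)/(0.20/0.80) = 1.71.

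Chance of a significant result in that direction, pooled two-proportion test, with d = p1 − p2:

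p̄ = (n1·p1 + n2·p2)/N; se0 = √[p̄(1 − p̄)(1/n1 + 1/n2)]; se1 = √[p1(1 − p1)/n1 + p2(1 − p2)/n2]; P = Φ[(d − 1.96·se0)/se1].

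Example: n1 = 199, n2 = 797, p1 = 0.30, p2 = 0.20. Then p̄ = 0.22, se0 = 0.0328, se1 = 0.0354, and P = Φ[(0.10 − 0.0643)/0.0354] = Φ(1.01) = 0.84.

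The unit matters. Sample Size Estimation calls the 996 participants, while the interim-analysis section calls them encounters. Aim 3 compares patients. At three evaluations each (the average in Sample Size Estimation), 996 encounters are 996/3 = 332 patients.

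| N | IR share (n1 / n2) | 25% vs 20% | 30% vs 20% |
|---|---|---|---|
| 996 | 20% (199 / 797) | 35% | 84% |
| 996 | 5% (50 / 946) | 15% | 41% |
| 332 | 20% (66 / 266) | 15% | 43% |
| 332 | 5% (17 / 315) | 9% | 20% |

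The normal approximation is rough in the last row. With assumed baselines of 10% to 30% and a 10-point shift at N = 996, the range is 76–95% at 20% IR and 33–59% at 5% IR. A range this wide shows that the assumptions drive the answer.

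**The case against.** The strongest reply is that the order of paperwork is not the order of observation. The sheet compiles what routine evaluation has already produced, partly from the medical record, so history, examination or imaging may have been charted before anyone read the valve. In the MRI pathway a different person may take the first reading. A reading alone does not show IR until it is compared with the documented setting. The family's symptom answer is blinded, and the Aim 3 paragraph does not say which source supplies symptoms. The data sheet is an attachment that is not in the text reviewed, so its layout or instructions may already help.

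All of this stands as a limit on the point, but none of it closes the gap. The protocol neither requires nor records that findings precede the reading. Nothing stops MRI staff passing the result to the team. The sheet itself carries the settings needed to recognise IR. The questionnaire does not cover staff-recorded signs or ventricular findings.

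Two stronger readings are tempting. A reader might infer that the whole Aim 3 endpoint is routinely recorded unblinded; the blinded questionnaire item and the compilation of earlier data do not support that. A reader might also take the percentages above as the plan's false-positive rate; they rest on an assumed baseline, assumed shifts and an unsettled unit of analysis.

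**Conclusion.** The point holds for staff-recorded signs, symptoms and ventricular findings. As written, the plan allows them to be recorded with knowledge of IR status, and any resulting bias would tend to favour hypotheses 3a and 3b. Its size is unknown, and it will not be uniform across encounters. The conclusion rests on the protocol text alone and assumes that the attached sheet carries no instruction that already separates the items. This is a cheap improvement to Aim 3; it does not touch the Aim 1 frequency and is no ground for discarding Aim 3.

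**What to change.** 1. Put the signs, symptoms and ventricular items in a section of the data sheet that is completed before the valve reading is disclosed to the person recording them. Where MRI staff read the valve first, this means that the recorder is not told until that section is done. The ventricular item waits for the images, again before disclosure.
2. Add a tick-box for whether the recorder, or the reader of the imaging, already knew the reading. A routine imaging report should not be assumed to be blind.
3. In Statistical Considerations, name the source of symptoms for Aim 3, and use the family's blinded questionnaire answer as a supporting symptom outcome for hypothesis 3a.
4. Repeat Aim 3 without the encounters recorded with the reading known, and report how many were excluded by IR status. Those encounters may differ clinically from the rest, so this is a sensitivity analysis and does not replace the main comparison.

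Clinical care is unchanged where the reading is needed first; the box is ticked and the encounter stays in the main analysis. The cost is a revised form and a small change in workflow, with no added staff or procedure. Some encounters will remain unblinded, and that should be stated as a limitation of Aim 3.

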### *Personnel Performing Evaluations*

Most research evaluations will be performed by the members of the neurosurgical team at ACH as part of their routine clinical care. We anticipate the questionnaire administration and pre-imaging valve checks may be performed by delegated care providers when patients are undergoing MRI evaluations prior to their typical contact with the neurosurgical team.

We anticipate MRI staff being our delegated providers for questionnaire administration and the initial valve setting check. We have discussed this role for the MRI staff with the Chief of Radiology and the radiology staff, none of whom believe their role in this study will add significant time or burden to their current responsibilities. Some current MRI staff have been checking Strata valve settings for many years in order to facilitate patient care. They do not anticipate significant difficulty training additional personnel in MRI.

As part of this study, all participating MRI staff (technologists and nurses) will receive standardized training by the principal investigator, neurosurgeons or neurosurgical advanced practice providers prior to evaluating the Strata valve unsupervised. We plan to train all appropriate staff, to check their proficiency, and for the neurosurgical staff to be available in case of questions or uncertainties at all times (there is 24/7 neurosurgical provider coverage at ACH). We do not anticipate difficulties in training our delegated study personnel: valve checks are quite easy, quick and painless for the patient. In fact, non-medical personnel can be trained in a matter of minutes on the proper technique to check a valve setting.

### *Patient/Family Questionnaire and Initial Shunt Valve Check*

Patients (or their parents) will complete the attached questionnaire, which was designed to evaluate the family's knowledge of the current valve setting.

Date: 4/19/2016 V.2  
Principal Investigator: [name]  
Application Number: IRB00093490

## **JHM IRB - eForm A – Protocol**

whether or not they feel the child is having symptoms of shunt malfunction, as well as their knowledge of the MRI susceptibility of their valve. Specific questions about the frequency and proximity of exposure to devices and circumstances that have previously been associated with IR will also be assessed.

Study personnel will check the valve setting, without divulging any information to the family about where the valve is currently set, in order to minimize patient or family bias when they are completing the questionnaire.

### *Shunt Data Sheet Completion by Study Personnel*

A wide range of clinical factors routinely gathered during neurosurgical evaluations will be recorded on a two-page data sheet at the time of each evaluation performed as part of this study. Data regarding documented valve settings, previous purposeful reprogramming, signs and symptoms of shunt malfunction, and the radiographic evaluation of the patient's ventricles will be recorded (see attached study personnel data sheet). Only factors routinely evaluated during typical neurosurgical evaluations will be recorded.

### *Data Storage and Entry*

Patients will be assigned a study identification number, and all data will be deidentified and kept in a locked location. Data will be entered into a secure password-protected database (REDCap) with PHI removed.

### *Minimal Additional Burden to Patients and Their Families*

It should be emphasized that this study is being performed during the routine evaluation and treatment of patients with Strata CSF shunts. The patient, the family and their health insurance provider will incur no additional charges as a result of participation in this study. We do not plan to recruit patients from outside the ACH system to seek care with us in order to participate in this study.

While completion of the questionnaire and data sheets are not part of the routine care rendered to a patient with a Strata CSF shunt, valve checks are a routine part of the care of all patients with a Strata CSF shunt. The current practice at ACH, and at most childrens' hospitals in the U.S., includes checking and making necessary adjustments to Strata valves each and every time a patient undergoes an MRI evaluation. As part of this study, we will also check (but not adjust) the shunt valve before an MRI is performed, in order to assess whether or not IR has occurred.

Date: 4/19/2016 V.2  
Principal Investigator: [name]  
Application Number: IRB00093490

## **JHM IRB - eForm A – Protocol**

Checking the valve setting transcutaneously before MRI is painless and quick (5-15 seconds).

We do not believe patients and their families will feel overly burdened by the extra valve check and the completion of the questionnaires. Most questionnaires will likely be completed by parents, which could be completed while their child is preparing for their MRI. Most patients and their families with Strata valves are accustomed to frequent valve pressure checks, with the vast majority of them not bothered at all by the process. We anticipate the addition of one additional shunt check will not prove burdensome or uncomfortable for them.

### **5) Inclusion/exclusion**

All patients with a Strata valve CSF shunt, who are 21 years of age or younger, will have the option to participate in this study. Patients who are over 21, those without a Strata valve CSF shunt, or those patients in whom the Strata valve is not checked prior to MRI scanning will be ineligible for the study. In addition, only patients who were evaluated by the neurosurgical service and returned to their normal environment more than seven days prior will be eligible to have their valves rechecked as part of this study.

### **6) Drugs/Substances/Devices**

A transcutaneous reprogramming device will be used to evaluate the magnetically susceptible CSF shunt devices. This is a quick and painless procedure. These valve-checking devices are currently distributed in many sites in the hospital and the outpatient facilities because they are used as part of the routine care of patients with Strata CSF shunts.

### **7) Study Statistics**

#### *Limited Previous Prevalence Studies*

The true prevalence and the implications of IR of programmable CSF shunts has not been previously defined or thoroughly studied. Most previous studies point to IR discovered during clinical evaluations for possible shunt malfunction, not evaluating each patient systematically regardless of their clinical status. Kestle *et al.* found that the Strata valve had an “unexplained change in performance level” 25 times in a total of 22 patients in their 315-patient multicenter study. More recently, Kondageski *et*

Date: 4/19/2016 V.2  
Principal Investigator: [name]  
Application Number: IRB00093490

## JHM IRB - eForm A – Protocol

al. from Great Ormond Street Hospital found that 7 of 24 (29%) patients closely followed with programmable valves were found to have had IR: two were believed to have been related to trauma and 5 had no identifiable cause. Other less comprehensive studies, which likely reported only accidental reprogramming that were discovered when a shunt malfunctioned, reported IR in 0% and 10% of patients.

Anecdotal information from ACH and other centers participating in the current study estimate that IR may be as high as 20% in patients without signs or symptoms of shunt malfunction based on evaluations that have been done outside of a formal study. Sample size estimates vary widely, depending on the true prevalence of IR we encounter. If IR is more frequent than we anticipated, we may obtain meaningful results with a smaller sample size than expected. Conversely, a lower prevalence of IR could result in larger sample size requirements. The duration of the study could be affected by the true prevalence of IR, which is largely unknown at this point.

### *Statistical Considerations*

The statistical analysis will be supervised and performed by [name] and his colleagues at the ACH/JHM CTRO. Demographic and clinical characteristics will be reported by IR status and compared using  $\chi^2$  or Fishers exact tests for categorical measures and t-test or Mann-Whitney U tests for continuous measures.

Aim #1: The frequency of IR will be calculated as the number of hydrocephalic children with Strata CSF shunt valves who had IR divided by the total number of hydrocephalic children with Strata CSF shunt valves.

Aim #2: The association between the field strength of MRI scanning and IR will be determined using unadjusted and adjusted generalized estimating equation models that account for multiple evaluations of participants. IR will be a binary outcome variable (IR present vs IR absent) and the field strength of MRI (3T vs 1.5T) will be the predictor variable. The adjusted model will include potential confounders that will be selected based on prior knowledge of factors established to be associated with IR as well as additional factors with p-value <0.1 in univariate analyses.

Aim #3: We will compare the proportion of patients with signs, symptoms or radiographic changes suggestive of shunt malfunction between the IR and no IR groups using  $\chi^2$  or Fishers exact tests for categorical measures and t-test or Mann-Whitney U tests for continuous measures

Aim #4: The association between devices that may have sufficient electromagnetic charge to affect programmable valves and IR will be determined using unadjusted and

Date: 4/19/2016 V.2  
Principal Investigator: [name]  
Application Number: IRB00093490

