### **4) Study Procedures**

#### *Participants*

Patients 21 years of age and younger, with Strata valve CSF shunts, who are being evaluated by the All Children's Hospital (ACH) neurosurgical service as part of standard of care, will be eligible for participation during the three-year enrollment period. Each time an eligible patient has contact with the neurosurgical service their valve will be checked for possible inadvertent reprogramming in the outpatient facilities, emergency department, and inpatient setting. Patients will have their valves checked as part of this study during each encounter. Only patients who were evaluated by the neurosurgical service and returned to their normal environment more than seven days prior to their current encounter will be eligible to have their valves rechecked as part of this study.

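### Aim 1 pools routine with emergency and inpatient contacts and ignores the number of checks per child, so its single figure cannot be read directly as the prevalence of inadvertent reprogramming (IR) whatever the symptoms

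*Combined protocol and SAP*

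**What the plan says.** The Aim 1 estimate is defined in Section 7, Statistical Considerations: "The frequency of IR will be calculated as the number of hydrocephalic children with Strata CSF shunt valves who had IR". The denominator is every child with such a valve, so this is a per-child proportion. It has no time window, no split by setting, symptoms or reason for visit, and no restriction to a first check.

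The data that feed it are described in Section 4, Participants. A child's "valve will be checked for possible inadvertent reprogramming in the outpatient facilities, emergency department, and inpatient setting", and this is repeated at every study contact. A recheck counts only if the child was seen and "returned to their normal environment more than seven days prior to their current encounter". Section 7, Sample Size Estimation, expects an average of at least three evaluations per child.

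The purpose is set by the criticism of earlier work in Section 7, Limited Previous Prevalence Studies: "Most previous studies point to IR discovered during clinical evaluations for possible shunt malfunction, not evaluating each patient systematically regardless of their clinical status". Section 3 likewise names the gap as a prevalence that does not depend on symptoms. Hypothesis 3a in Section 2 expects children with IR to have signs or symptoms of malfunction more often than children without it. Section 4, Shunt Data Sheet Completion by Study Personnel, has signs and symptoms recorded at each evaluation.

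**The concern.** Association runs both ways. If children with IR are more often symptomatic, then symptomatic children more often have IR, and contacts prompted by suspected malfunction carry more IR than routine ones. A single pooled proportion then moves with the share of symptom-driven contacts.

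The number of checks matters as well. A child counts as having had IR if it is found at any check, so frequent attenders have more chances to enter the numerator, and some of them may attend often because of symptoms. Aims 2 and 4 use generalized estimating equations to allow for repeated evaluations; Aim 1 has no such provision.

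At stake is how the main descriptive result is read. Section 3 says it should inform families and clinicians about avoiding household magnets and about replacing valves. A figure that depends on one service's contact pattern does not transfer directly to another.

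**Working it through.** **1. The plan's own precision.** Inputs from Section 7, Sample Size Estimation: n = 996, IR frequency 5%, 95% confidence interval.

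Half-width = 1.96 × √(0.05 × 0.95 / 996) = 1.35 points, which rounds to the stated 1.4. The figure reproduces.

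**2. Effect of contact mix (illustration).** The documents give neither a contact mix nor an IR rate by reason for visit, so these are assumptions. Take one check per child, so that the weights apply to children as in Aim 1. Set IR at 5% for routine contacts (borrowing the overall planning value) and at q for symptom-driven contacts, whose share is w.

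Pooled = (1 − w) × 5% + w × q, so the shift is w × (q − 5%).

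| q | Pooled, w = 10% | Pooled, w = 50% | w at which the shift reaches 1.4 points |
|---|---|---|---|
| 5% | 5.0% | 5.0% | never (shift 0) |
| 10% | 5.5% | 7.5% | 1.4 / 5 = 28% |
| 15% | 6.0% | 10.0% | 1.4 / 10 = 14% |

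**3. Effect of the number of checks (illustration).** Assume 5% IR per check and independent checks. The chance that a child is ever counted is 1 − 0.95^k:

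- k = 1: 5.0%
- k = 3 (the plan's minimum average): 14.3%
- k = 6: 26.5%

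The same per-check rate therefore gives quite different Aim 1 figures depending on attendance. Restricting to one check per child removes this effect.

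**4. Precision of separate estimates.** Same half-width formula, with routine IR 5% and symptom-driven IR 10%. Section 7 calls the 996 participants under Sample Size Estimation and encounters under Interim Analyses, so both readings are shown. At three evaluations each, 996 encounters are 996 / 3 = 332 children.

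| Children | Symptom-driven share | All, at 5% | Routine | Symptom-driven |
|---|---|---|---|---|
| 996 | 20% | ±1.4 | ±1.5 | ±4.2 |
| 996 | 40% | ±1.4 | ±1.7 | ±2.9 |
| 332 | 20% | ±2.3 | ±2.6 | ±7.2 |
| 332 | 40% | ±2.3 | ±3.0 | ±5.1 |

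**The case against.** A reader might infer that the study repeats the flaw it criticises. The documents do not support that. Earlier studies mostly looked for IR when malfunction was suspected and so could miss silent cases. Section 7 cites 0% and 10% from studies of that kind, against 29% (7 of 24) in a closely followed series. Here asymptomatic attenders are checked too. What remains is milder: symptom-driven contacts enter the figure undistinguished.

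A reader might also take the illustrative shifts as the size of a bias. They are not. The 5% is a planning value for overall IR, not a routine-visit rate, and the only figure for children without symptoms is anecdotal, up to 20%. Nor do the documents say that emergency or inpatient contacts are always prompted by suspected malfunction; clinic patients can have symptoms.

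A third inference is that the routine-visit figure should replace the pooled one as the headline. That is contestable. If IR causes symptoms, some affected children will present through unscheduled visits, and dropping them would understate IR. One selection would replace another.

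Finally, Aim 3 compares symptoms between IR groups, and if counts are shown, IR by symptom status could be worked out from them. This stands in part. The planned test does not itself give an IR frequency with an interval for children seen without suspected malfunction, and it does not deal with the number of checks.

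**Conclusion.** The point holds in a limited form. The Aim 1 proportion depends on the mix and number of contacts if IR is associated with symptoms, which the protocol itself hypothesises. It therefore should not be presented alone as the prevalence irrespective of symptoms.

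The size of the effect cannot be known from the documents. On the stated assumptions the mix effect can exceed the quoted precision at plausible shares of symptom-driven contacts, and it vanishes if IR does not differ between them. The rule of more than seven days between evaluations limits repeat checks within one episode but removes neither dependence. The case for change rests on a cheap remedy and a clearer estimate, not on a demonstrated bias.

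**What to change.** Keep the pooled Aim 1 figure. Add IR frequency with a 95% CI at each child's first eligible check, reported separately for contacts without suspected malfunction (routine or asymptomatic) and for symptom-driven contacts. Interpret the pooled figure alongside these. Classify by symptoms and reason for visit, not by setting alone.

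Symptoms are already recorded. A field for reason for visit is not visible in the documents, because the attached data sheet is not among them; add one if it is absent.

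The cost is a possible extra data field, a short table and wider intervals in the strata, slight for the routine estimate and larger for the smaller symptom-driven group. Using one check per child avoids the clustered intervals that a per-encounter split would need. The conflict over whether 996 counts participants or encounters is a separate matter, but it must be settled before any Aim 1 precision is quoted.
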